8.2.3 Intervention(s)

DORA uses a variety of AI technologies to deliver the patient follow-up call, including: speech transcription, natural language understanding, a machine-learning conversation model to enable contextual conversations, and speech generation. Together, these technologies cover the input, processing and analysis, and output needed to maintain a natural conversation. **DORA** is configured to deliver calls through a telephone connection as a real-time, stand-alone system: the operator inputs individual patient details to initiate the call and completes a summary in the electronic health record (EHR) afterwards. The call that patients will receive from **DORA** will include several conversational elements:

- Greeting and introduction
- Identification of patient
- Cataract follow-up questions
- Patient's queries
- (Decision)
- Questions about acceptability
- Closure of call

The entire conversation will be supervised by a clinician. This clinician will be able to interrupt the call at any point if the system fails, the patient struggles to interact with it, or **DORA** does not collect sufficient information from the patient. The call will proceed in the following stages (visualised in Figure 5):

- 1. Stage 1. Call initiation: the supervising clinician will confirm the suitability of the patient, input their details, and initiate the call.
- 2. Stage 2. Symptom assessment: Once the call has begun, **DORA** will verify the identity of the patient and proceed through the cataract follow-up questions. As the patient answers the questions, both **DORA** and the supervising clinician will record their independent assessment about the clinical significance of the symptoms elicited.
- 3. Stage 3. Management plan decision: Once all of the follow-up questions have been asked, **DORA** and the supervising clinician will independently make and record their decisions about the management plan for the patient. **DORA** will then inform the patient of the clinician's decision about their management plan (i.e. whether specialist review is required or not).
 - Stage 3a: Optionally, if required, the supervising clinician can ask additional clarifying questions.

Figure 5. Flow Diagram of DORA's call with patient

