8.2.4 Comparator(s)

Imperial sees all of their post-operative cataract patients at a face-to-face out-patient appointment with an ophthalmologist or specialist nurse. This is conducted between three to four weeks following the procedure. Therefore, patients at Imperial will receive their call from **DORA** within 3 days before their scheduled appointment (day 25-27 post-surgery). This will enable the results of the **DORA** call to be compared with the face-to-face appointment at Imperial to assess whether any complications were correctly identified and if the management plan remains the same.

For patients at both clinical sites, health records will be examined 90 days after the call to determine if the patient presented to an eye clinic with any complications from surgery. This comparison of the follow-up with actual complication rate will enable an assessment of **DORA's** safety (see Table 6).

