8.2.5.2 Secondary Outcomes

There will be several secondary outcome measures to assess the clinical safety, feasibility, usability, and acceptability of the system (see Table 6).

Clinical safety

To examine safety, two outcomes will be captured. Firstly, patients at both sites will have a retrospective case review of both general and ophthalmic electronic health records at 90 days after their initial operation. Complications will be identified from patient's medical records related to any unplanned eye-related clinical episode.

Secondly, all cataract surgery patients at Imperial were historically followed up face-to-face between 3-4 weeks post-surgery in a dedicated post-op clinic. Any complications requiring a change in patient management at slit lamp review or from attending eye casualty services (as the Oxford site does not normally perform face-to-face follow-ups) will be compared with the decisions made by **DORA** and the clinician. If Imperial changes their method of follow-up due to the COVID-19, assessment for complications will be done by checking hospital medical records as is done at the Oxford site.

Feasibility

Feasibility will be assessed by examining the proportion of autonomous calls that were completed without needing any intervention from the supervising clinician. All interruptions or clarifying questions of the supervised call will be logged; the supervising clinician will be asked to log the reason for asking clarifying questions. If clarifying questions were asked because the clinician felt that there was insufficient information for either individual symptoms or to make a management plan, the clinician's management plan before and after clarifying questions will be captured to see if clarifying questions changed the management plan.

Usability

Usability will be assessed using questions presented to patients following calls delivered by online and paper surveys distributed to participants. These questions will be drawn from the System

Usability Scale (SUS) and Telehealth Usability Questionnaire (TUQ; see 13.4 Appendix 4 for a sample survey) [14,15].

Acceptability, satisfaction, and appropriateness

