DORA's acceptability, satisfactoriness, and appropriateness will be assessed during qualitative interviews with a subset of the patients. These semi-structured interviews will provide an opportunity for patients to provide more in-depth feedback about what they liked about **DORA** and any barriers to use that they experienced during the call (see 13.5 Appendix 5 for a sample topic guide). The supervising clinician will also be asked to provide feedback about their level of satisfaction with the system and any safety concerns they might have.

Patients' willingness to recommend **DORA** to others will also be assessed at the end of the call [20]. **DORA** will calculate a net promoter score (NPS) by asking patients "on a scale of 1 to 10, how likely would you be to recommend this automated service to a friend or colleague." **DORA** will follow up by asking patients to "tell me why you gave that score."

Cost-effectiveness

Cost-effectiveness will be examined by collecting and analysing health economic data before and during the study. The costs of implementing **DORA** will be compared with historical data about the costs of the usual standard of care.

| Secondary Outcome | Outcome Measure | | | |
|-----------------------|---|--|--|--|
| Clinical Safety | Complications identified from patients' electronic health records up to 90 days following cataract surgery | | | |
| | Congruence between complications identified and management planned in DORA call and face-to-face follow up (Imperial) Comparison to data from patients attending eye casualty (Oxford) | | | |
| Feasibility | Proportion of autonomous calls that were completed without needing any intervention from the supervising clinician | | | |
| | Clinician-reported reasons for asking clarifying questions | | | |
| Usability | System Usability Scale (SUS) [14,17] | | | |
| | Telehealth Usability Questionnaire (TUQ) [15] | | | |
| | Qualitative feedback from semi-structured interviews | | | |
| Acceptability | Qualitative feedback from semi-structured interviews | | | |
| Satisfaction | Qualitative feedback from semi-structured interviews, Net Promoter Score (NPS) | | | |
| Appropriateness | Qualitative feedback from semi-structured interviews | | | |
| Cost-effectiveness | Comparison of the costs of implementing DORA and the costs of the usual standard of care | | | |
| Identify improvements | Synthesis of all of the outcome measures previously described | | | |

Table 6. Secondary Outcome Measurement

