8.4.2 Blinding

No blinding of participants will be done in the study, as all eligible patients will receive the same intervention. The clinicians listening to the call will be blinded to **DORA's** decisions when they are making their own assessments.

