8.4.3 Methods of Data Collection

8.4.3.1 Quantitative data collection

The key data to be collected are **DORA** and the clinician's decisions. This will include data on symptoms as well as an overall assessment. Both **DORA** and the clinician will separately record their decisions about symptoms, clinical assessment, and management plan. **DORA** will record the decisions in the **DORA** database, which will be accessed by the study team during the evaluation to compare against the clinician decisions. Usability of the system will be assessed using the SUS and

TUQ questionnaires (see 13.4 Appendix 4). These will be delivered to all participants shortly after they have had the call with **DORA** via an online or paper survey (see Figure 6).

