8.5 Data Analysis

8.5.1 Statistical Methods for Primary Outcome

The primary analysis will be the calculation of a kappa statistic of inter-observer (**DORA** & clinician) reliability of the decision made. Additionally, the outcome of the assessment will be compared with the 'real' complication rate determined by hospital medical records. This will be established by identification of any hospital presentation within 90-days after the last call. Given the specialist nature of ophthalmology services it can be assumed that patients will present through the eye casualty or clinic services offered by each site. Patients who present to the hospital eye service will be analysed on a case-by-case basis to ensure that complications that were missed by **DORA's** original assessment and complications that developed later can be differentiated. This analysis will provide baseline sensitivity and specificity data for use in preparing subsequent evaluations of efficacy.

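### Protocol 8.5.1 separates missed from later complications with no stated masking and no matching test for flagged patients, and the SAP has no such split

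*Protocol*

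**What the plan says.** Protocol 8.5.1 compares DORA's assessment with complications found in hospital records. "Patients who present to the hospital eye service will be analysed on a case-by-case basis", so that complications missed at the call and "complications that developed later can be differentiated. This analysis will provide baseline sensitivity and specificity data". The judgement is thus part of how sensitivity and specificity are obtained.

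The source is a "retrospective case review of both general and ophthalmic electronic health records at 90 days after their initial operation" (8.2.5.2). On masking, 8.4.2 says: "The clinicians listening to the call will be blinded to" DORA's decisions. It names nobody else. DORA's decisions are held in its own database, "which will be accessed by the study team during the evaluation to compare against the clinician decisions" (8.4.3.1). Section 8.2.3 adds that the operator of the call "completes a summary in the electronic health record (EHR) afterwards".

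The SAP, dated 30 August 2022 (the protocol's submission version is dated 17 May 2021), lists the clinical safety comparison under secondary outcomes. It cross-tabulates DORA's outcome with three yes/no variables: hospital review within three months, unexpected change in management, and unplanned hospital review. It has no onset date and no missed-or-later variable.

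**The concern.** Whether a complication was already present on the day of a phone call is often a matter of judgement. Here the answer decides whether a patient DORA passed counts as a false negative. The plan gives no criteria for that judgement, does not say who makes it, and does not say that this person is kept from knowing DORA's result.

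The split is also lopsided. Missed has meaning only for patients DORA passed. For a flagged patient with a later complication, nothing requires the reviewer to ask whether it was there at the call, so that patient can stay a true positive by default.

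Baseline sensitivity and specificity for postoperative complications are the second objective in 7.5. The limitations section (8.6) relies on the 90-day record check to mitigate the lack of routine review at Oxford. A sensitivity that depends on an unmasked, undocumented sorting step would be a weak base for the later evaluations it is meant to inform.

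**Working it through.** **The plan's own figures.** The documents give no expected number of complications and no target sensitivity. The stated sample size of 520 reproduces as precision for a single proportion: 1.96² × 0.25 / 0.03² = 1067.1, then 1067.1 / (1 + 1066.1/1014) = 520.2. It was not set for sensitivity. The planned 591 is used below only as a denominator.

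**The two reference standards for a DORA-negative patient**

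| Event in the records | Protocol 8.5.1 | SAP |
|---|---|---|
| Judged present at the call | False negative | False negative |
| Judged to have arisen later | Set apart from the misses | False negative |

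The SAP matches 8.5.1 only if the judgement is made when its three variables are coded. Neither document says that it is.

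**Formulas.** Let TP and FN be the true positives and false negatives with all events counted. Let k be the DORA-negative events moved to later, and a the flagged events that also arose after the call.

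- All events counted: TP / (TP + FN)
- Split applied to DORA-negative patients only: TP / (TP + FN − k)
- Split applied to everyone: (TP − a) / (TP − a + FN − k)

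The second expression exceeds the first whenever k > 0, masked or not. The third need not.

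**Assumed illustration.** Take 50 complications, 40 flagged and 10 passed. Fifty in 591 is 8.5%. The small site audits span 1/30 = 3.3% (the attendance at 10 weeks, Appendix 7) to 7/25 = 28% (management changes at face-to-face follow-up, Appendix 6, where the printed percentage is 21%).

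- No relabelling: 40/50 = 80%
- k = 3: 40/47 = 85.1%
- k = 6: 40/44 = 90.9%
- k = 10: 40/40 = 100% by construction

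If the same share of flagged events were also found to be later, the gain would vanish. At 30% (a = 12, k = 3) the result is 28/35 = 80%. At 60% (a = 24, k = 6) it is 16/20 = 80%. Equal shares are only an assumption, since flagged events may more often have been present at the call. It shows that the outcome depends on a question the plan does not ask.

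**Sensitivity to the event count.** At 2/30 = 6.7% (both late Oxford contacts), about 39 events are expected in 591. With an assumed sensitivity near 70%, 27/39 = 69.2% (95% CI 52.4–83.0) becomes 27/36 = 75.0% with three relabelled and 27/33 = 81.8% (64.5–93.0) with six. At 3.3%, about 20 events, 14/20 = 70.0% becomes 14/17 = 82.4% with three.

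**Specificity.** With 39 events, 40 assumed false positives and six cases moved from false negative to true negative, specificity goes from 512/552 = 92.8% to 518/558 = 92.8%, a change under 0.1 point.

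**How many cases need judging.** Section 8.2.4 says "health records will be examined 90 days after the call to determine if the patient presented to an eye clinic", while the secondary outcome table reads "Complications identified from patients' electronic health records up to 90 days following cataract surgery". With the Imperial call on days 25–27, the window closes on day 90 or on days 115–117. The longer window admits more late events to be sorted.

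**The case against.** The strongest reply is that the SAP is the later document and contains no split. Followed literally, the ten misses in the illustration stay ten and sensitivity stays 80%. This stands, and it limits the claim: the route operates only if the judgement in 8.5.1 is applied or enters when the SAP's variables are coded. But a literal SAP drops the separation that the protocol promises and counts truly late events as misses. The disagreement therefore remains either way.

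Three stronger readings are tempting, and the documents do not support them.

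- A reader might infer that the reviewer learns DORA's result from the call summary in the health record. No section says the summary shows DORA's own decision. That decision goes to a separate database, and the patient is told the clinician's decision. The documented route is the study team's access to the database, and even there the documents do not say that those people do the 90-day review. Masking is unstated; it is not shown to be absent.
- A reader might infer that unmasked review must favour DORA. Each relabelling does raise sensitivity, but that follows from the split itself. A reviewer who knows the result could also call a truly late event missed, which lowers sensitivity.
- A reader might treat the whole rise from 80% to 85–91% as distortion. If those complications did arise after the call, the higher figure is the better estimate on that side of the table. Late events are plausible: the Oxford audit records contacts at 6 and 10 weeks.

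Two points of scale also stand. The comparison is secondary, since the primary analysis is agreement with the clinician masked to DORA. At Imperial (286 of the 591 planned), a face-to-face visit is due within three days of the call, so little onset judgement is needed there unless COVID-19 changes follow-up. The issue bears mainly on Oxford (305) and on events after the Imperial visit.

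**Conclusion.** The concern holds as a question of design and reconciliation. Protocol 8.5.1 lets an undefined case-by-case judgement, with no stated masking, remove false negatives from the sensitivity estimate, and it does not put the same question to flagged patients. The SAP uses a different reference standard. Knowledge of DORA's result may influence the judgement, in either direction.

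The documents do not allow the size of any bias to be estimated. The move from 80% to 85–91% assumes 50 complications, 10 of them passed by DORA, and 3 to 6 of those relabelled wrongly. With the 20 to 39 events implied by the Oxford audit rates, three judgements move the estimate by about 6 to 12 points. Specificity is barely affected by moving false negatives. The change is worth making because it is cheap and protects the main safety estimate from this comparison; it does not touch the primary agreement analysis.

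**What to change.** Name who does the 90-day review. For every presenting patient, flagged or not, that person records complication type, onset date and whether the complication was likely present on the call date. DORA's decision and the supervising clinician's decision are hidden. Symptoms recorded at the call may stay visible, because they are direct evidence on onset. The record is locked before DORA's decision is linked.

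Add the variable to the SAP and report sensitivity and specificity twice: with all 90-day events counted, and with only those judged present at the call. This reconciles 8.5.1 with the SAP and shows how far the result depends on the judgement. State one starting point for the 90 days in both documents.

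The cost is one extra data-preparation step to hide the decisions and a few added fields. No more participants are needed and treating staff are unaffected. Masking may be incomplete where later clinic notes mention the result of the call.

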8.5.2 Other Data Analyses

The usability and acceptability questions delivered to patients via online or paper surveys after the completion of the call will be analysed quantitatively based on the scales' scoring criteria - for instance, a score above 80 on the System Usability Scale is generally considered to indicate an above average user experience [17]. The semi-structured interview recordings will be transcribed and assessed using thematic analysis.

8.6 Limitations

There are a couple limitations with the protocol. First, the number of issues identified during routine follow-up at the two sites cannot be directly compared. Unlike Imperial, Oxford does not proactively review patients following uncomplicated cataract surgery, instead relying on patients to self-present to the eye casualty service. This introduces a potential risk for missed complications if **DORA** decides

that a clinical review is not needed. However, this risk is minimised by the safety net established by the expert clinician oversight of the call and is a part of the current standard of care at the Oxford NHS Trust. The limitation is also mitigated by the examination of patient records after 90 days to identify any complications that might have been missed.

The second limitation is related to generalisability. The evaluation will only include patients who had uncomplicated cataract surgeries. This focus on routine care is important for establishing the feasibility of **DORA**, but means that **DORA**'s effectiveness for dealing with post-operative follow-up of complex patient groups cannot be assessed in this study. The National Ophthalmology Database (NOD) audit report however shows that the most common complication of posterior capsule rupture occurs in only 1-2% of patients [3].

Technical limitations of the system also affect generalisability. At present, patients with cognitive difficulties, hearing impairment or non-English speakers are not able to use **DORA** and will not be included in the study. However, this reflects the same limitations as human telemedicine services.

Finally, potential bias is introduced to the results by the use of qualitative interviews because of the influence of the interviewer on how participants respond (e.g. social desirability bias). This potential bias will be assessed by examining the balance of positive and negative feedback and by comparing the qualitative and quantitative data about **DORA's** usability.

8.7 Generalisability

Limitations to the generalisability of the study results were noted in the previous section. However, it is expected that the results will be generalisable to the majority of cataract surgery patients. The vast majority of cataract surgeries are uncomplicated; only approximately 2.5% of cataract surgeries have intraoperative complications (which would have resulted in exclusion from this study) [3]. Therefore, if the results of this study are positive, they will demonstrate **DORA's** potential to manage almost all cataract surgery follow-up assessments.

9 ETHICAL AND REGULATORY CONSIDERATIONS

9.1 Assessment and Management of Risk

Risks will be monitored on a weekly basis via the project management process and mitigated by Risks/Actions/Issues/Decisions log.

The Covid-19 pandemic has raised potential issues for recruitment for the study. To address this risk, an ethics submission will enable remote informed consent if restrictions prohibit face-to-face contact.

Risks regarding the system include it failing to detect patients who require urgent clinical review - this will be mitigated by having a clinician supervise the call in real-time, able to intervene if needed. The risk of lack of trust in the system has been mitigated by an extensive co-creation process for **DORA** that focused on user-centred design.

The interviews are scheduled to take place for between 20 to 30 minutes in order to mitigate time risk to participants. The nature of interview questions avoid areas of cultural or psychological sensitivity and are purely focused on impact of the intervention. Since Brexit, the General Data Protection Regulation (GDPR) no longer applies to the UK; however, it has been incorporated in UK domestic law [22]. To control any potential perceived issues in this area, participant confidentiality will be protected using data protection procedures that are compliant with the Data Protection Act 2018 (DPA 2018) [23]. For more details about data protection and patient confidentiality plans for this study, see section 9.7.

9.2 Research Ethics Approval

Ethical approval is being sought from the Health Research Authority and the relevant Research Ethics Committee with this submission [24]. As the IRAS system brings together these assessments, only one application is needed [24]. The protocol will therefore receive medical device review from the associated REC.

HRA approval is the ethical approval route used for studies with NHS patients at both Imperial College London and the University of Oxford [25,26]; additional independent ethical approval will be sought from the University of Plymouth. At the University of Plymouth, an application for ethical approval will be submitted through the Plymouth Ethics Online System (PEOS) to the Health Faculty Research Ethics and Integrity Committees (FREIC) [27].

Imperial College London, as the study sponsor, will ensure that the study has received ethics approval from a research ethics committee (REC) and has received Health Research Authority (HRA) approval.

